Appendix	
Mapping and Ablation procedure	
Patient questionnaire	

Introduction and purpose of the study

Neuro-mediated cardioinhibitory syncope (SCNM) represents the most frequent form of syncope in the young population without apparent cardiac or neurological pathology (1,2). Although affected young patients have an excellent prognosis, their quality of life can be seriously deteriorated by the frequency of episodes (2,3,4). Definitive cardiac pacing is an effective therapy and is recommended in patients >40 years old (1,2,5,6); there are no trials in patients <40 years old. The general scientific consensus is that in younger patients the role of the pacemaker raises some concerns arising from the need for numerous replacements and possible ventricular remodeling induced by right ventricular pacing over time.

In patients <40 years old with severe recurrent syncope, current practice is to implant loop recorders in order to document the dominant mechanism of syncope, cardioinhibitory or vasodepressor. In cases of asystolic syncope, in the absence of proven effective therapies, recently, transcatheter radiofrequency ablation of the anatomical site areas of the ganglionic plexuses in the right and left atrium has shown promising results, both in the short and long term regarding the treatment of cardioinhibitory reflex syncope (7,8,9,10,11,12,13,14). In Italy, ganglion plexus ablation, so-called cardioneuroablation (CNA) has been current practice in selected cases since 2012 at Policlinico Casilino (15) and the results have been published recently (13). The technique proposed by Caló et al (13), consists of ablation of the ganglionic plexuses of the right atrium. No center currently has sufficient case series to establish long-term efficacy and safety results, for which a multicenter interventional study is therefore needed.

[figure not shown]
In view of these premises, the aim of the study will be to evaluate the efficacy and safety of NAC in patients with SCNM with ECG documentation of spontaneous asystolic episodes of reflex nature.

Study design

ItalianCNA is a multicenter Italian interventional "proof of efficacy" clinical trial that aims to evaluate the incidence of asystolic pauses and heart rate in patients with SCNM who performed CNA after documentation of asystolic pauses on ECG monitoring by implantable loop recorder.

The study is independent, "investigator-initiated," sponsored by a nonprofit scientific association called the Italian Multidisciplinary Group for the Study of Syncope (GIMSI).

Inclusion criteria

- Age between 18 and 60 years
- Patients with a clinical diagnosis of neuromediated syncope according to class I criteria of the ESC guidelines, Table 1
- Clinical history of recurrent syncope (≥2 in the last year or ≥3 in the last 2 years), severe, not tolerated by the patient
- Documentation of ≥2 asystolic pauses >3 sec daytime on ECG monitoring by implantable loop recorder (ILR), with or without syncope
- Refusal by patient to perform pacemaker implantation

Recommendations	Class	Level
Reflex syncope		
 VVS is highly probable if syncope is precipitated by pain or fear or standing, and is associated with Typical progressive prodrome (pallor, sweating, nausea). 	I	С
 Situational reflex syncope is highly probable if syncope occurs during or immediately after specific triggers. 	I	С

Table 1. Diagnostic criteria of reflex syncope according to ESC guidelines (1,2)

Tilt test is recommended but not mandatory. Patients with negative tilt test are also enrollable. It can be either positive or negative.

Exclusion criteria

- Absence of sinus dysfunction and atrioventricular node disease.
- Absence of structural heart disease
- Possible alternative diagnoses of syncope

Ablative procedure

The ablative procedure involves applying radiofrequency deliveries in the two Right atrium anatomical sites close to the two main ganglionic plexuses of the right atrium:

- **Inferior-posterior area (site of first ablation)** corresponding to the right inferior atrial ganglion located between the inferior vena cava, coronary sinus ostium and near the atrioventricular node
- **Upper-posterior area (site of second ablation)** corresponding to the right superior atrial ganglion located between the superior vena cava and the posterior surface of the right atrium

The method of the ablative procedure is described in detail in the Appendix (see)

Acute success is defined as:

- Shortening of AH interval >20 ms, relative to baseline, persisting for 30 min, and/or Wenckebach point <500 ms at end of procedure plus
- P-P interval <70% of basal P-P interval, or P-P interval <600 ms (calculated as the average of 10 consecutive cycles), after 10 min since the last delivery

The procedure will be continued until the acute efficacy criteria are met. In case the procedure is terminated without having reached the target, this will be noted as "acute failure"

Follow up (study phase)

It consists of remote monitoring and quarterly questionnaire completed by the patient himself (see appendix).

 Remote monitoring. Central, by an ad hoc established Single Laboratory. All episodes of asystole >3 sec and average monthly heart rate will be recorded

• Patient's self-administered questionnaire. The syncope follow-up questionnaire validated in the BioSync study (6) will be used. Every 3 months the patient will send the questionnaire to the Single Laboratory.

An "Adjudication Committee " consisting of 3 physicians not involved in the study will validate ECG events and questionnaire responses

Endpoint

Main analysis according to intention-to-treat principle. Exploratory subgroup analysis with acute success.

Primary endpoint: Intrapatient comparison of monthly incidence of episodes. asystolic >3 sec before and after CNA

Secondary endpoints:

- Intrapatient comparison of mean heart rate, before and after CNA
- Intrapatient comparison of monthly incidence of (pre)syncopal episodes before and after CNA
- Intrapatient comparison of beat-to-beat variability of heart rate in the short term (spectral analysis) before and after CNA (limited to auxiliary HRV study)

Ancillary substudy (ancillary study): spectral analysis

It consists of acquiring digitized ECG monotrace for 5 minutes the day before and the day after the procedure using surface ECG recording equipment provided free of charge by the promoter. Spectral analysis of the oscillatory components of R-R interval variability will be performed on the ECG trace. This study is optional

Sample calculation

Considering clinically effective a 50% reduction in the monthly incidence of asystole episodes of >3 sec, which before the ablative procedure is assumed to be 0.82 ± 0.67 (16), with 24 patients undergoing ablation, the null hypothesis (Ho: null difference in asystole incidence pre/post-ablation) can be rejected with 80% statistical power at a two-sided t-test with alpha error 0.05.

Bibliography

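### Patients are selected on recent syncope count, and the (pre)syncope endpoint has no defined pre-CNA window; if the qualifying history is used, its syncope component falls with no treatment effect

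*Protocol*

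**What the plan says.** Under Inclusion criteria, the Protocol requires a history of recurrent syncope, "≥2 in the last year or ≥3 in the last 2 years". A separate criterion concerns pauses: "Documentation of ≥2 asystolic pauses >3 sec daytime on ECG monitoring by implantable loop recorder (ILR), with or without syncope".

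Under Endpoint, one of the three secondary endpoints is "Intrapatient comparison of monthly incidence of (pre)syncopal episodes before and after CNA". No section says which period, or which source of data, supplies the pre-CNA value.

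Symptom data are described under Follow up (study phase): "It consists of remote monitoring and quarterly questionnaire completed by the patient himself (see appendix"). The same section adds "Every 3 months the patient will send the questionnaire to the Single Laboratory" and places validation of the responses by the Adjudication Committee there. No symptom collection before CNA is described.

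Study design describes one group, patients ablated after pauses were recorded: "in patients with SCNM who performed CNA after documentation of asystolic pauses on ECG monitoring by implantable loop recorder". No control or reference group appears anywhere. Only the Protocol is at hand; an SAP may exist.

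**The concern.** A patient enters because the recent syncope count is high. Part of a high count is a lasting tendency and part is chance, and the chance part is not expected to recur. Over the window through which a patient qualifies, the rate cannot be below 3/24 = 0.125 per month (or 2/12 = 0.167 by the one-year route). No such floor applies after CNA. If the qualifying window is also the comparator, some fall in syncope is built in, and without a control arm it cannot be separated from an effect of the procedure.

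This route is distinct from the pause criterion, which bears on the primary endpoint. Changing the pause baseline would leave it in place.

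(Pre)syncope is the only listed endpoint that measures what patients feel, in a trial described as proof of efficacy. An SAP can define a window, but it cannot recover pre-CNA questionnaire data that were never collected. The choice therefore has to be settled in the Protocol, before patients are ablated.

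**Working it through.** **The plan's own figure.** No figure is given for this endpoint. Sample calculation covers only the primary endpoint: "with 24 patients undergoing ablation" and "80% statistical power at a two-sided t-test with alpha error 0.05". With a difference of 0.5 × 0.82 = 0.41 per month, and 0.67 taken as the SD of the paired difference (an assumption), a paired t-test has 80.1% power with 23 patients and 81.9% with 24. The figure reproduces, and this point does not affect it. Only n = 24 is carried forward.

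**Inputs.** The entry rule is from Inclusion criteria. The Protocol gives no syncope rate, so the yearly rates λ below are assumptions. There is no treatment effect in any scenario.

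**Constant rate, last year as the pre-CNA period.** Let X1 and X2 be the counts in the last year and the year before, both Poisson(λ). A patient qualifies if X1 ≥ 2 or X1 + X2 ≥ 3. The pairs (X1, X2) that fail are (0,0), (0,1), (0,2), (1,0) and (1,1). Hence

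- P(qualify) = 1 − e^(−2λ)(1 + 2λ + 1.5λ²)
- E[X1 | qualify] = [λ − e^(−2λ)(λ + λ²)] / P(qualify)
- apparent fall = 1 − λ / E[X1 | qualify], because the expected count after CNA is still λ

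For λ = 1: P(qualify) = 1 − 4.5 × 0.1353 = 0.391; E[X1 | qualify] = (1 − 2 × 0.1353)/0.391 = 1.865; fall = 1 − 1/1.865 = 46%.

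| True rate per year | P(qualify) | Pre-CNA mean, qualifiers | Post-CNA mean | Apparent fall |
|---|---|---|---|---|
| 1 | 0.391 | 1.865 | 1 | 46% |
| 2 | 0.799 | 2.367 | 2 | 16% |
| 3 | 0.949 | 3.129 | 3 | 4% |

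Using both qualifying years as the pre-CNA period gives 41%, 14% and 4%, so a longer history does not remove the effect.

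**Between-patient variation.** With personal rates gamma-distributed (shape 1.5, mean 2 per year), simulation gives a fall of about 11%. Across a wider grid (gamma shapes 0.5, 1 and 2, and no variation; one- or two-year window) the fall runs from 25% to 72% at a source mean of 0.5 per year and from 0.2% to 2.3% at 5 per year. It was positive in every scenario.

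**Chance of a significant result.** The Protocol names no test for this endpoint. Borrowing a paired t-test with n = 24, rejection under no effect is about 81%, 15% and 6% at constant rates of 1, 2 and 3, and 12% in the gamma (shape 1.5) case, against a nominal 5%.

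**Adding presyncope, which is not selected on.** Assume one independent presyncope per syncope, counted in both periods. The pre-CNA mean is E[X1 | qualify] + λ and the post-CNA mean is 2λ:

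- λ = 1: 1 − 2/2.865 = 30%
- λ = 2: 1 − 4/4.367 = 8%
- λ = 3: 1 − 6/6.129 = 2%

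The gamma case falls by about 6%.

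**Syncope-only history against (pre)syncope afterwards.** Under the same one-to-one assumption the ratio post/pre is 2/1.865 at λ = 1 and 4/2.367 at λ = 2. These are rises of 7% and 69% with no effect of any kind.

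**Separate pre-CNA window.** With the pre-CNA year drawn independently of the qualifying years, the spurious change is −0.4% to 0.5%. A false significant improvement then occurs in 2.2% to 2.6% of trials, which is the nominal one-sided level.

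**The case against.** The strongest reply is that the Protocol never names the qualifying history as the pre-CNA value. It defines no pre-CNA window for any endpoint, such windows are often left to an SAP, and every patient has a loop-recorder period before CNA that could serve. This stands: the bias is conditional on the qualifying window being used. What remains is that no other source of pre-CNA symptom data is described, and nothing written prevents that use.

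A reader might therefore infer that the endpoint, as written, must fall under an ineffective procedure. The Protocol does not support that. The window is undefined, presyncope dilutes the effect, and a history without presyncope set against a follow-up that counts it could move the other way.

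A reader might also take the 46% fall and 81% rejection as the size of the problem. They need every patient to share a true rate of 1 per year. The Protocol gives no rate and describes the syncope as severe, and at 3 per year the effect is slight.

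Nor can the change from recalled history to an adjudicated questionnaire be counted as a further push towards a fall. It makes the periods less comparable, but its direction is unknown.

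Finally, the loop-recorder period is not a clean substitute. It is selected on at least two pauses, some of which may accompany syncope. It may lie within the qualifying year. Because the pauses must be documented before a patient is eligible, it is already past at enrolment.

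**Conclusion.** The point holds in conditional form. The Protocol selects on syncope count, compares (pre)syncope before and after CNA in one arm, leaves the pre-CNA window undefined, and describes no pre-CNA symptom count other than the qualifying one. If that count is the comparator, the direction for the syncope component is certain: it falls with no treatment effect.

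The size is uncertain because it rests on assumed rates: about 46%, 16% and 4% at 1, 2 and 3 syncopes per year, about 11% in the gamma case, and roughly 30%, 8% and 2% for the combined count with one presyncope per syncope. Neither the size nor the direction for the combined endpoint can be fixed from the Protocol alone.

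The matter goes beyond missing detail, because data not collected before ablation cannot be supplied later. It should be corrected, but it is confined to a secondary endpoint.

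**What to change.** Change the Endpoint and Follow up sections as follows.

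1. State that the qualifying syncope history is not the pre-CNA comparator for this endpoint, and report it descriptively.
2. Count the same event types in both periods, with syncope and presyncope shown separately. The questionnaire has room for one episode and one date, so it would need to be completed per episode.
3. Where a pre-CNA period outside the qualifying window exists, collect it with the same questionnaire items and the same adjudication. Acknowledge that a loop-recorder period is itself selected on at least two pauses, and that symptoms in it are recalled if it precedes enrolment.
4. Where no such period exists, present the before/after change as descriptive and not as evidence of efficacy. Report post-CNA syncope and presyncope incidence with a confidence interval.

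The wording costs little, and the questionnaire items already exist. The price is a pre-CNA window that is shorter, less precise or absent for some patients, and a weaker secondary claim. A fully prospective pre-CNA window would need earlier enrolment or a run-in, which is a larger change and is not required for items 1, 2 and 4.

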Appendix

Mapping and Ablation procedure

The day before ablation procedure, an ECG is performed in resting conditions and after intravenous administration of atropine. Atropine test is carried out in fasting state with up to 2 mg intravenous atropine sulfate, under continuous ECG recording for 30 minutes (two injections of 1 mg atropine with an interval of 5 minutes). A decrease more than 25% in PP interval is accepted as a positive response.

Mapping and ablation are performed under mild sedation and local anesthesia. Three right femoral vein punctures are performed: a) a decapolar catheter is inserted into the coronary sinus; b) a quadripolar catheter is positioned in the hisian region; c) and a quadripolar deflectable irrigated tip ablation catheter (Navistar SmartTouch, Biosense Webster, Inc or Tacticath, Abbott Inc) is used for mapping and ablation. Electroanatomical mapping of the right atrium (RA) is performed by means of CARTO 3[™] (Biosense Webster, Inc) or by EnSite Precision (Abbott Inc). A three-dimensional anatomical mapping of the RA is performed, during which volume data are recorded continuously during manipulation of the catheter inside the RA. From the outer surface of the volume data acquired, the system generates a surface reconstruction. Tagging the phrenic nerve capture points on the lateral RA allowed us to map the phrenic nerve course. The parameters considered during basal electrophysiological study are: basal cycle length, AH interval and Wenckebach cycle length.

The ablation procedure consists of RF delivering (RF energy at 43°, 30-35 W for 30-60 s) at right atrial anatomic sites where the underlying presence of GP clusters is regarded as highly probable: 1) **the inferior-posterior area** (**first ablation site**): inferior right GP placed between inferior vena cava, coronary sinus ostium and near the atrio-ventricular groove, 2) **the superior-posterior area** (**second ablation site**): superior right atrial GP, adjacent to the junction of the superior vena cava and the posterior surface of RA. The identification of the anatomical target is improved by the

presence of high amplitude fractionated electrograms (HAFE, number of deflections \Box 4, amplitude \Box 0.7 mV and duration \Box 40ms) by using of a single beat analysis in order toquantify number of signal deflections and total activation time and differentiating them by normal electrograms (number of deflections < 4 or duration < 40 ms).

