Care is taken to avoid ablations in the proximity of the mapped course of the phrenic nerve. To avoid phrenic nerve injury, high amplitude stimulation is performed just before radiofrequency delivery to the superior right atrial GP.

Considering that the exact anatomic borders of GP clusters are unknown, an expanded number of RF applications are delivered in order to form a cloud-like shape ablation surrounding the HAFE tags. An irrigated tip catheter using a contact force >5 g is recommended. P-P interval is carefully monitored. The duration of each single ablation is generally prolonged for at least 30 seconds after stabilization of P-P intervals but does not exceed 60 seconds at the same location. RF applications are interrupted if no significant shortening of the P-P interval is observed within 30 seconds or an ablation index target value of >350-500 or lesion stability index target

value of 4-5.5 is achieved. Points acquired during ablation are annotated by 2 mm tags.

It is recommended that ablation is continued until atrial electrical activity (HAFE) is significantly reduced (peak to peak bipolar electrogram < 0.05 mV) and vagal reflex disappears if present.

It is also recommended, at the end of ablation procedure, to confirm the significant reduction of atrial electrical activity by using of a final voltage map and by showing inability to capture at high output. In addition, a backup stimulation in the right ventricle is performed through a quadripolar catheter in case of prolonged asystolic response evoked during RF.

Basal cycle length, AH and Wenckebach cycle length are reassessed after RF ablation.

After catheter removal, atropine 2 mg (1m + 1m 5 min later) is administrated intravenously > 30 minutes after the last ablation.

Acute procedural **success** is defined as:

 Persistent AH shortening > 20 msec and/or persistent reduction in Wenckebach point cycle length < 500 msec

and

 Post RF P-P interval <70% of the baseline procedural P-P interval or P- P interval >600 msec after 10 minutes of waiting time (as mean value of 10 consecutive cycles)

Post RF inappropriate sinus tachycardia is temporarily treated with beta-blockers or ivabradine.

Patient questionnaire

PATIENT QUESTIONNAIRE

Patient ID:

CNA-----

Date of completion (dd-mm-yyyyy): _____-

QUESTIONNAIRE		
(a) Did you completely lose consciousness for a moment? (syncope, fainting)	☐Yes □ No	

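### The AV-node limb of acute success is defined in two ways: the body tests the final Wenckebach value against 500 ms with no baseline reference, while the Appendix asks for a reduction

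*Protocol*

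**What the plan says.** The protocol defines acute success in the section Ablative procedure and again at the end of the Appendix on mapping and ablation. Both versions require an AV-node limb and a P-P limb.

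- **Body, AV-node limb:** "Shortening of AH interval >20 ms, relative to baseline, persisting for 30 min, and/or Wenckebach point <500 ms at end of procedure plus". The AH part is a change from baseline. The Wenckebach part is a level, read when the procedure ends.
- **Appendix, Wenckebach part:** a persistent "reduction in Wenckebach point cycle length < 500 msec". This is worded as a change, with no minimum size.
- **P-P limb:** both versions offer a relative route, which the body gives as "P-P interval <70% of basal P-P interval", and an absolute route at 600 ms.

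The definition has two uses. In Ablative procedure it ends the intervention: "The procedure will be continued until the acute efficacy criteria are met", and a case that stops short is recorded as an acute failure. Under Endpoint it defines the one subgroup that the protocol names: "Exploratory subgroup analysis with acute success". The main analysis there is by intention to treat.

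The Wenckebach value is measured at both times. For the basal study the Appendix says "The parameters considered during basal electrophysiological study are: basal cycle length, AH interval and Wenckebach cycle length", and for afterwards "Basal cycle length, AH and Wenckebach cycle length are reassessed after RF ablation". No entry criterion sets a minimum basal Wenckebach value.

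**The concern.** The two parts of the AV-node limb are joined by and/or, so either one suffices. In the body, a final Wenckebach value below 500 ms therefore meets the limb whatever the patient's starting value was. Someone who was below 500 ms at the outset and did not change passes. The Appendix, by asking for a reduction, would not pass that patient.

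Two things are at stake. First, this is a multicentre study, and operators apply the criterion during the procedure. Sites working from different pages can record success and failure for the same measurements. Second, the acute-success subgroup can contain patients in whom no AV-node change was measured, although the first ablation site lies close to the AV node. In a study planned for 24 patients, a few such patients can alter a subgroup noticeably.

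**Working it through.** The plan gives no figure on this point to reproduce. The planned 24 patients serve below only as a denominator.

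**Step 1. Apply each wording to the same measurements.** The Appendix phrase can mean a fall to below 500 ms (the natural reading) or a fall by less than 500 ms (the literal one). The patients are constructed, and the post-RF value is taken as the persistent, end-of-procedure value in every version.

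| AH (ms) | Wenckebach (ms) | Body | Appendix: fall to <500 | Appendix: fall by <500 |
|---|---|---|---|---|
| 80→80 | 450→450 | met | not met | not met |
| 80→80 | 450→470 | met | not met | not met |
| 80→80 | 480→479 | met | met | met |
| 80→80 | 560→480 | met | met | met |
| 80→80 | 560→520 | not met | not met | met |
| 110→80 | 560→560 | met | met | met |

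Rows 1 and 2 are the discordant cases: the body passes an unchanged or lengthened value, and neither reading of the Appendix does. Row 5 shows that the literal reading adds a disagreement in the other direction. Row 3 shows that a 1 ms fall satisfies the Appendix, so adopting its text as it stands would not settle what counts as a change.

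**Step 2. Carry this to acute success.** The P-P limb must also be met. A patient who meets it by the relative route meets it in both versions. For that patient, rows 1 and 2 become acute success under the body and acute failure under the Appendix.

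**Step 3. Bound the number of discordant patients, on the natural reading.** Let q be the share with basal Wenckebach below 500 ms and e the share with an AV-node change sufficient to meet the limb by change. The protocol gives neither. Assume that q and e are independent and that values below 500 ms at baseline stay below.

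- Upper bound: 24 × q.
- Discordant on the AV-node limb: 24 × q × (1 − e). This falls further by the share who do not meet the P-P limb.
- Share of AV-node passes in the body without such a change: q(1 − e) / [q + (1 − q)e].

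| q | 24 × q | Discordant, e = 50% | Discordant, e = 80% | Share of passes, e = 50% | Share of passes, e = 80% |
|---|---|---|---|---|---|
| 10% | 2.4 | 1.2 | 0.5 | 9% | 2% |
| 25% | 6 | 3 | 1.2 | 20% | 6% |
| 50% | 12 | 6 | 2.4 | 33% | 11% |
| 75% | 18 | 9 | 3.6 | 43% | 16% |
| 90% | 21.6 | 10.8 | 4.3 | 47% | 18% |

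Worked line for q = 50%, e = 80%: 24 × 0.5 × 0.2 = 2.4, and 0.5 × 0.2 / (0.5 + 0.5 × 0.8) = 0.10 / 0.90 = 11%.

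**The case against.** The strongest reply is that this is loose drafting with little consequence. The body refers to the Appendix for the detailed method, so its line may be a shortened form of the Appendix text. Basal and final values are both recorded, so either definition can be applied later. The subgroup is only exploratory. Much of this stands, and it limits the size of the point. It does not remove it: both texts set out the criterion in full, neither is said to govern, and the decision to end the procedure is taken on the day and cannot be reclassified afterwards.

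A reader might infer more than the protocol supports:

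- **That such a patient meets the criterion before any ablation.** The body times the test at the end of the procedure; the value is merely below the threshold already. The inferior-posterior area is still the first ablation site, and the Appendix separately recommends endpoints based on electrogram reduction and loss of any vagal reflex.
- **That a low Wenckebach value alone gives acute success.** The P-P limb is required as well. Its absolute route runs in opposite directions in the two texts (the Appendix has "P- P interval >600 msec after 10 minutes of waiting time"), but that is a separate discrepancy.
- **That the subgroup cannot answer its question.** The protocol states no question for it and does not say that it must show an AV-node effect. Its meaning is blurred, which is a weaker statement.
- **That 6, 12 or 18 patients would be misclassified if the share below 500 ms were 25%, 50% or 75%.** Those counts include everyone below 500 ms at baseline. Only those with no qualifying AH or Wenckebach change and a met P-P limb are classified differently.

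**Conclusion.** The point holds as a conflict between two versions of an operative criterion. A patient with a basal Wenckebach value below 500 ms, no AH shortening beyond 20 ms and no Wenckebach fall meets the AV-node limb in the body and not in the Appendix. With the P-P limb met, that patient is a success on one page and a failure on the other.

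The size cannot be derived from the protocol. On the natural reading of the Appendix it is at most the number of patients below 500 ms at baseline. The tabulated scenarios run from under 1 to about 11 of 24 before the P-P limb is applied, and they rest on assumed shares and on independence. The consequences are confined to classification at sites, the criterion for ending the procedure, and the exploratory subgroup. The primary intention-to-treat comparison and the sample size do not depend on it. An amendment is worthwhile, but the trial's main result is not in question.

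**What to change.** Reconcile the acute-success text in Ablative procedure with that in the Appendix, so that one definition applies at every site. It should state whether the Wenckebach part requires a change from the recorded basal value and, if so, how that change is expressed, so that the two readings of the Appendix phrase no longer compete. Which rule is clinically right is for the investigators; this review does not choose one.

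For the analysis, report how many patients had a basal Wenckebach value below 500 ms, and show the exploratory acute-success result under both classifications as a sensitivity analysis.

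The cost is a wording amendment and a little extra analysis, with no new data, since the basal and post-RF values are already collected. The subgroup may be smaller under one version.

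### The loop-recorder pauses that qualify a patient also count in the 'before' rate, so the uncontrolled pre/post test expects some fall even if CNA does nothing

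*Protocol*

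**What the plan says.** Protocol, Inclusion criteria, asks for "Documentation of ≥2 asystolic pauses >3 sec daytime on ECG monitoring by implantable loop recorder (ILR), with or without syncope". No time frame is attached.

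Protocol, Study design, describes patients "who performed CNA after documentation of asystolic pauses on ECG monitoring by implantable loop recorder". Every patient is treated, and no control group is described.

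Protocol, Endpoint, sets the primary endpoint as "Intrapatient comparison of monthly incidence of episodes. asystolic >3 sec before and after CNA", with the main analysis by intention to treat. The start and end of 'before' are not given.

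Protocol, Follow up (study phase), provides central remote monitoring: "All episodes of asystole >3 sec and average monthly heart rate will be recorded". This is the follow-up after CNA. The only loop-recorder monitoring described before CNA is the one that documents the qualifying pauses.

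Protocol, Sample calculation, takes 0.82 ± 0.67 episodes per month before ablation and sets the benchmark: "Considering clinically effective a 50% reduction in the monthly incidence of asystole episodes of >3 sec". It then states that "the null hypothesis (Ho: null difference in asystole incidence pre/post-ablation) can be rejected with 80% statistical power" with 24 patients and a two-sided t-test at 0.05.

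**The concern.** The event that admits a patient is also the event that is counted. Each 'before' count that covers the qualifying period is at least two by construction, while the 'after' count carries no such condition. Patients tend to enter after a cluster of pauses, and their rate then drifts back towards its usual level whatever is done to them. Because there is no comparator, nothing cancels this drift, and a zero pre/post difference is not the same hypothesis as no CNA effect.

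Two things are at stake in a single-arm trial meant as proof of efficacy: the false-positive rate of the primary test, and the honesty of the estimated reduction when it is read against 50%.

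**Working it through.** **The plan's own figure.** The target difference is 0.5 × 0.82 = 0.41 per month. If 0.67 is taken as the SD of the within-patient difference, a paired two-sided t-test at 0.05 (noncentral t) has 80.1% power with 23 patients and 81.9% with 24. The stated 24 reproduces and is not at fault here.

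**Inputs.** From the protocol: 0.82 ± 0.67, n = 24, at least 2 qualifying pauses, two-sided 0.05. Assumed, because the protocol gives none: Poisson pauses, gamma-distributed patient rates, 12 months of post-CNA recording, all pauses daytime, and the waits and look-backs below. The gamma shape is k = (0.82/0.67)² = 1.498 and the scale is θ = 0.82/1.498 = 0.547. The true CNA effect is set to zero.

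**Case 1: the whole recorder period counts.** For a patient with rate λ, the time T to the second pause is Gamma(2, λ). M further pauses occur in the wait w before CNA, and the 'before' rate is (2 + M)/(T + w). As w approaches 0 its expectation is E[2/T] = 2λ, twice the true rate; recording after qualification dilutes this. By simulation:

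| Wait w (months) | 0.5 | 1 | 2 | 3 | 6 |
|---|---|---|---|---|---|
| Apparent fall, no effect | 25% | 17% | 10% | 7% | 3.5% |
| Two-sided rejection | 28% | 19% | 11% | 8% | 6% |
| of which favouring CNA | 28% | 19% | 11% | 8% | 5% |
| True fall that reads as 50% | 33% | 40% | 44% | 46% | 48% |

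The last row is 1 − 0.5/(1 − apparent fall). For w = 1: 1 − 0.5/0.83 = 40%.

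**Case 2: fixed look-back of W months, at least two pauses in it.** Counts are negative binomial. For W = 12:
- θW = 6.57 and q = 6.57/7.57 = 0.868.
- P(0) = 7.57^(−1.498) = 0.0482; P(1) = k·q·P(0) = 0.0627; P(2) = k(k+1)/2·q²·P(0) = 0.0680.
- P(N ≥ 2) = 1 − 0.0482 − 0.0627 = 0.889.
- Expected 'before' rate = (0.82 × 12 − 0.0627)/(12 × 0.889) = 0.916.
- True mean rate of those selected = (0.82 − 0.0627/12 − 2 × 0.0680/12)/0.889 = 0.904.
- Apparent fall = 1 − 0.904/0.916, about 1%.

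The same sums for W = 3 and 6 give 1.361 against 1.156 (15%) and 1.055 against 1.000 (5%). Rejection at 3/6/12 months is about 33/9/5%. The 3-month cell implies a 'before' rate of 1.36, well above the 0.82 that the protocol expects, so it fits the protocol's figures poorly.

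**Does a long recording period remove it?** Not by itself. In Case 1 the mean window is 2k/((k − 1)μ) + w, where μ is the mean rate. At 0.82 ± 0.67 and w = 0.5 it is 2 × 1.498/(0.498 × 0.82) + 0.5 = 7.8 months, with a 25% fall. At an assumed lower rate of 0.40 ± 0.30 (k = 1.778) it is 2 × 1.778/(0.778 × 0.40) + 0.5 = 11.9 months, with a fall of about 33%.

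**Counting only after qualification.** If the clock starts once the second pause is past, the expected 'before' rate equals the true rate and the mean fall is 0% at every wait tried. Subtracting the two pauses but keeping their time over-corrects: with a constant rate of 0.82 and a 12-month window it gives 0.65.

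**The case against.** **The window is undefined, and an SAP that is not shown may define it.** This stands as a limit on size: the results run from about 1% to 25% on waits and windows that are assumed. It does not remove the point. The entry event, the outcome event, the uncontrolled contrast and the zero null are all fixed in the protocol, and together they produce the bias unless something is done about it.

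**The result depends on the summary used.** This is correct. The bias towards CNA belongs to per-patient rates, which an intrapatient t-test uses. With varying patient rates, a whole-period rate pooled over events and time errs the other way, at about 0.5 to 0.7 of the true rate.

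**Selection cannot reach the 50% benchmark.** This largely stands. A reader might infer that a positive trial could be wholly an artefact of selection. At 0.82 ± 0.67 with the whole period counted, an observed fall of 50% or more without any effect occurs in fewer than 1% of simulated trials at a 0.5-month wait and almost never from 1 month on. A fixed look-back of about one month would come close (45% with gamma rates, 65% with a constant rate). It would need a 'before' rate above 2.3 per month, and nothing in the protocol points to it.

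**A long window cures it.** A reader might infer this from the fixed look-back results. It holds for a fixed look-back of about 12 months, or for many months of recording after qualification. It fails for a long recorder period that closes soon after the second pause.

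**Conclusion.** The point holds. With per-patient rates, the protocol's primary comparison has an expected difference above zero when CNA has no effect, and almost all excess rejections favour CNA. At 0.82 ± 0.67 with the whole recorder period counted, the false-positive rate is several times 5% only when CNA comes within about a month of the second pause; it is 11/8/6% at 2/3/6 months. A 12-month look-back leaves almost nothing. The estimate is inflated to a matching degree.

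The direction follows from the protocol's own rules. The size rests on Poisson pauses, gamma rates, 12 months of follow-up and assumed timings, so confidence in any single figure is moderate.

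The documents do not support the further inference that no efficacy claim may be made unless a post-qualification comparison succeeds: at short waits that comparison has too little power to act as a gate. The point should be fixed, but it does not invalidate the design.

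**What to change.** In the Endpoint section:

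1. Fix the start and end of the 'before' window before any post-CNA data are read.
2. Keep all treated patients in the main intention-to-treat comparison.
3. Pre-specify a sensitivity comparison, reported beside it with a 95% CI: pauses >3 s per recorder-monitored month from the day after the second qualifying pause to CNA, against the post-CNA rate. A rate model with a log monitored-time offset and patient-level robust standard errors is preferable. Count and report patients with no monitored time in that interval.
4. Where at least 12 months of pre-CNA recording exists, a fixed look-back of that length is an alternative, with about 1–2% bias at the protocol's rate (5–6% at 0.40 ± 0.30).
5. State that the main pre/post fall contains a selection component, and interpret it together with the sensitivity result.

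**Cost.** Wording and one added analysis; no new procedure and no change to CNA dates. The added comparison is noisy at short waits. At 0.82 ± 0.67 and 0.5/1/2 months, 70/52/33% of patients have no pause in the interval. Power for a true 50% fall is then about 23/50/81% by paired t-test, or 51/72/91% by the rate model. It also assumes that further pauses do not move the CNA date. If half the patients with a third pause had CNA brought forward to 0.5 months after it (an assumption), a spurious fall of about 13–16% would return at maximum waits of 2 to 6 months.
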